The objective of this study is to determine if incidence of chronic neuropathic pain (CNP) varies as a function of anesthetic technique in patients undergoing inguinal herniorrhaphy surgery at VAPHS, hypothesizing that a total intravenous anesthetic (TIVA) protocol utilizing propofol and lidocaine will result in a lower incidence of acute and chronic neuropathic pain (ANP and CNP, respectively) than an inhalational anesthetic based protocol.

This is a patient-blinded, prospective, randomized study. Forty-eight patients undergoing either inguinal (including femoral) or ventral (including umbilical) herniorrhaphy that requires general anesthesia in the operating room will be enrolled. Exclusion criteria include: those unable to communicate directly with the investigators, a history of disease that prevents anesthetic randomization, the presence of any pain-related disorders such as fibromyalgia, and the need for emergency surgery. Patients will be assigned to one of three anesthetic technique protocols: TIVA with ketamine (TIVA-K), TIVA with remifentanil (TIVA-R), or Balanced Inhalational Anesthesia (BIA, consisting of an inhaled anesthetic only) using a computer-generated random numbers table. Sixteen subjects will be used in each group.

The medications administered in the operative room will be recorded. Study data will include the pain numerical rating scale (NRS, the traditional 0-10 pain score where 0 indicates no pain and 10 equates to the most intense pain imaginable) at rest and with movement, the revised version of the short form McGill Pain Questionnaire (sf-MPQ), the self-report of the Leeds Assessment of Neuropathic Symptoms & Signs (s-LANSS), and the Pain Quality Assessment Scale (PQAS). These will be collected during the pre-operative assessment, in the PACU prior to discharge, approximately 24 hours post-operative, 1 months post-operative, 3 months post-operative, 6 months post-operative, and 12 months post-operative.

3.0 * Describe the study objectives. Please include primary aim and hypothesis, if applicable any secondary aims and hypotheses.**Objective and Specific Aims**

To determine if incidence of chronic neuropathic pain (CNP) varies as a function of anesthetic technique in patients undergoing inguinal herniorrhaphy surgery at VAPHS.

Primary Aim

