The initial data will also consist of baseline measurements of the outcome variables to establish baseline values. These will consist of the study's primary endpoints: the pain numerical rating scale (NRS, the traditional 0-10 pain score where 0 indicates no pain and 10 equates to the most intense pain imaginable), and the revised version of the short form McGill Pain Questionnaire. Additionally, the study's secondary endpoints will be collected: the self-report of the Leeds Assessment of Neuropathic Symptoms & Signs (s-LANSS), and the Pain Quality Assessment Scale (PQAS). The NRS is being used as it will allow us to compare our results with those of historical studies that only used this numerical score. Additionally, in the initial post-operative assessment, it is believed that subjects will not have yet recovered the mental faculties necessary for the more involved scales. The revised short form McGill Pain Score Questionnaire (sf-MPQ-2) is considered by many to be the "gold standard" pain questionnaire, especially for neuropathic pain. The s-LANSS has been shown to discriminate neuropathic from non-neuropathic pain; a score of greater than 12 is considered to be indicative of neuropathic pain (4). Finally, research has shown that the PQAS is able to assess pain changes during and as a result of treatment.

Intra-operative data recorded will include the total amounts of all medications documented on the Anesthesia Record, the surgical approach used (laparoscopic versus open), the type and location of the hernia being repaired, and details on any local anesthetic infusions used by the surgery team.

Follow-up data will be collected at six time points in person or over the phone per convenience including a) post-operative prior to Post Anesthesia Recovery Unit discharge, b) 18-36 hours post-operative, c) 1 months post-operative, d) 3 months post-operative, e) 6 months post-operative, and f) 12 months post-operative. Additional data collected will include details about analgesic use at all time points.

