All outcome variables (NRS, s-LANSS, PQAS, sf-MPQ) are ordinal data, and as such will require non-parametric testing. As the study is progressing, the techniques will be compared via Kruskal-Wallis testing at each time interval. The presence of CNP will be defined as a positive S-LANSS (scores ≥ 12 are highly suggestive of neuropathic pain); after the 3 month time point will be considered "chronic". These definitions are consistent with the literature and with published standards.(2,4) Thus, for the 6 and 12 month time points, the incidence of CNP for each technique will be computed and compared via chi-squared analysis.

Interim analyses are planned for 3, 6, 9 and 12 months, with the major focus being a definitive power analysis for variables found to be non-significant (as this is a pilot study). Because this study involves no changes to standard of care for herniorrhaphy surgery patients, stopping the study prematurely based on these interim analyses is not expected.

As planned, a continuous sampling of patients undergoing umbilical or inguinal herniorrhaphy will be included in this study. In addition, all equipment and personal required for this study are already in place within the VAPHS. Therefore, time for patient enrollment or equipment procurement is not necessary, and this study can begin as soon as all approvals (including IRB, R&D and ACOS) are granted. The study will continue for at least 1 year. The decision to continue past this time will be based on the achieved statistical power after 12 months of data collection. Because the data will be entered throughout the year and analyzed at 3 month

intervals, the time required for final analysis will be minimal. Submission for publication is expected within 3 to 12 months of the completion of data collection.

ID: Pro00000878

View: 5 Sub-Studies

1.0 * Is there a sub-study or are there sub-studies associated with this study?
There is no sub-study associated with this study.

ID: Pro00000878

View: 6 Study Population Summary

Study Population Summary

1.0 * What is the maximum number of subjects you plan to enroll at VAPHS?
60

2.0 * Do you plan on enrolling patients into different categories:
 Yes **No**

If yes, please explain:

3.0 If this is a multi-site study, indicate the projected total subject accrual:

4.0 * Please provide a justification for the sample size:

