This waiver is only being requested for screening and recruitment purposes. Patient involvement will be considered complete after the final questionnaires are administered 12 months after surgery. The results of the study will then be compiled, analyzed, described, and published. While any practical effect the type of anesthesia each individual patient received would have little impact on the patient's future medical history, the study's published results will be available electronically.

ID: Pro00000878

View: 9.3 Waiver of Documentation of Informed Consent

Waiver of Documentation of Informed Consent**You have selected a waiver of Documentation of Informed Consent****1.0 This is a request for Waiver of Documentation of Informed Consent because this research study conforms to either A and/or B (Check if 'yes' and provide the verifying information requested):**

* A: The only record linking the subject and the research would be the consent document and the principal risk would be potential harm resulting from a breach of confidentiality. Each subject will be asked whether the subject wants documentation linking the subject with the research, and the subject's wishes will govern. Yes No

AND/OR

* B: The proposed study poses minimal risk to the subjects. Yes No

If yes, please explain why the proposed study poses minimal risks to the subjects. (Outline the subject's involvement in the project and why the study poses minimal risk) :

This study will pose minimal risk to the subjects since all anesthetic techniques are within the standards of best practice for patients undergoing herniorrhaphy with general anesthesia. The proposed intervention will not alter surgical modality as previously determined by the treating physician. The backbone of the study is the collection of the data via the survey instruments, which carries only the very rare risk for a breach of confidentiality. The precautions detailed in the risk section will be used to minimize this risk.

2.0 * The research involves no procedures for which written consent is normally required outside of the research context. Research procedures include:

For this waiver, the procedures only include the sharing of information of interested patients with the PI so that he can contact the potential subject and further describe the study. All subjects that participate in the full study will review and sign an informed consent document.

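### Continuation past month 12 rests on an achieved power with no stated effect or threshold; read as power at the observed effect, it only restates the p-value

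*Combined protocol and SAP*

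**What the plan says.** View 4.1 (analysis plan, item 1.0) schedules interim analyses at 3, 6, 9 and 12 months. Their main purpose is "a definitive power analysis for variables found to be non-significant (as this is a pilot study"). The next paragraph sets a minimum duration, "The study will continue for at least 1 year", and then the rule for going further: "The decision to continue past this time will be based on the achieved statistical power after 12 months of data collection".

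The same section makes CNP incidence across three arms the primary outcome, tested as follows: "Thus, for the 6 and 12 month time points, the incidence of CNP for each technique will be computed and compared via chi-squared analysis". It also plans running comparisons of the pain scales: "As the study is progressing, the techniques will be compared via Kruskal-Wallis testing at each time interval". View 4 (Data Collection) instead calls the NRS and the short-form McGill questionnaire the primary endpoints. It lists the s-LANSS, the scale that defines CNP, as secondary.

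The target is 48 patients, 16 per arm (View 4.1). The maximum enrolment is 60 (View 6, item 1.0). Early stopping on the interim results is described as not expected. Each patient is followed for a year: "Patient involvement will be considered complete after the final questionnaires are administered 12 months after surgery" (Views 9.2 and 9.3).

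**The concern.** A decision about the study's length or size is tied to a quantity that the plan does not define. No effect size, power target or formula is given, and the two sections that could identify the endpoint disagree.

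The wording points towards power at the observed effect, since it is computed for results already found non-significant and no planned effect exists. That quantity adds nothing to the p-value and varies widely in small samples. Power for a chosen effect would be legitimate, but it needs no interim data by arm and could be settled before the first patient. Either way the rule does not guide the decision it is meant to guide. A pilot intended to support a larger study (View 7.1) would also pass on a poor basis for sizing it.

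**Working it through.** The plan states no power figure, so there is none to reproduce. It supports the target of 48 by citing earlier studies of 43, 34 and 45 subjects.

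**Inputs from the documents:** alpha 0.05; 16 per arm (48 in all); ceiling 60, or 20 per arm; chronic pain incidence 10% to 63%; CNP tested by chi-square at 6 and 12 months. **Assumed here:** an 80% power target, the effects shown, and even accrual without dropout.

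**1. Power at the observed effect.** Observed power = P(X > c), where X is noncentral chi-square with noncentrality equal to the observed statistic and c is the 5% critical value.
- p = 0.05: 50% (1 df), 58% (2 df).
- p = 0.20: 25% (1 df), 34% (2 df).
- 80% requires a statistic of 7.85 (1 df, p about 0.005) or 9.63 (2 df, p about 0.008).

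Observed power rises only as p falls. A non-significant result therefore never exceeds 50% or 58%, whatever the data.

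**2. Its spread.** Exact enumeration of the three-arm test, CNP 50% in BIA and 20% in each TIVA arm:

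| Patients per arm | True power | Observed power, 5th to 95th percentile |
|---|---|---|
| 4 | 10% | 5% to 72% |
| 8 | 26% | 8% to 84% |
| 16 | 46% | 11% to 95% |

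**3. Power for a chosen effect.** CNP halved in both TIVA arms. The three-arm columns are exact enumeration of the Pearson chi-square; the pooled columns compare BIA with both TIVA arms combined.

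| BIA rate | Three-arm, 48 | Three-arm, 60 | Pooled, 48 | Pooled, 60 | Total for 80%, three-arm |
|---|---|---|---|---|---|
| 10% | 6% | 7% | 12% | 13% | about 1,080 |
| 30% | 16% | 21% | 25% | 28% | about 310 to 320 |
| 63% | 47% | 54% | 57% | 66% | about 105 |

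At 60 patients, 80% is reached only for very large effects, such as 63% down to about 22%.

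**4. Data available at month 12, counted from study start.** Patient i (0 to 47) enters at i × A/48 months.
- 6-month data need i × A/48 + 6 ≤ 12. This gives 48, 25, 17 and 13 patients for A = 6, 12, 18 and 24 months.
- 12-month data need i × A/48 + 12 ≤ 12. This gives one patient, i = 0, in every case.
- The last 12-month survey falls at 47A/48 + 12, about month 18 (A = 6) to month 36 (A = 24).

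**5. Type I error.** 1,000,000 simulated trials per case; equal CNP of 10%, 30% or 63% in all arms; looks at 16 then 20, or 8 then 16, per arm.
- Stop and claim only at 80% observed power, otherwise test at the end: 3.5% to 5.5%.
- Claim an unadjusted p < 0.05 at either look: 5.4% to 9.2%.
- Single final test, for reference: 3.5% to 5.3%.

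**6. Precision of interval estimates at a 30% rate.**
- Two arms of 16: 1.96 × √(2 × 0.3 × 0.7/16) = 0.32.
- Pooled rate, 48 patients: 1.96 × √(0.3 × 0.7/48) = 0.13.

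**The case against.** The best defence is that this is a declared pilot with enrolment capped at 60, early stopping not expected and little error inflation. View 4.1 names CNP as primary, so the endpoint has a natural default. The halving is an effect chosen here, and power for the ordinal scales has not been worked out. Much of this stands and limits the severity. But pilot status explains the lack of a prior power calculation; it does not define a data-dependent rule. The default endpoint is weakened by View 4.

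Three stronger readings are tempting and not supported.
- **The two meanings of power give opposite decisions on the same data.** For the halving, that needs observed power of 80%, hence p of about 0.008 or less on 2 df. Such a result lies outside the non-significant variables that the interim power analysis addresses. For p above 0.05, both meanings fall below 80%.
- **Follow-up could be cut off at study month 12.** View 4 schedules surveys at "d) 3 months post-operative, e) 6 months post-operative, and f) 12 months post-operative", and Views 9.2 and 9.3 agree. Continuing most naturally means further enrolment, although the plan does not say so.
- **The rule seriously inflates type I error.** The figure of about 9% needs an unadjusted claim at an interim look, which the plan does not propose.

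**Conclusion.** The point holds as a defect in method and definition, of minor to moderate weight. With no effect or threshold and an unsettled endpoint, the continuation rule cannot be applied as written. As observed power, it reports every non-significant variable as underpowered against any target above 58%, and it is too variable to steer by. As power for a chosen effect, it is known in advance, and for a halving of CNP it cannot reach 80% within the ceiling of 60. A decision at study month 12 could rest at most on 6-month CNP data, apart from about one patient.

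The power figures depend on the assumed effects and base rates, and the timing on even accrual without dropout. That observed power restates the p-value depends on none of these.

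**What to change.** In View 4.1, replace the continuation sentence with:

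> Enrolment ends at 48 randomised patients (16 per arm); any places between 49 and 60 only replace patients lost to follow-up, decided without outcome data by arm. Every patient is followed to the 12-month survey. The confirmatory CNP comparisons at 6 and 12 months are made once, after the last 12-month survey.

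Replace the post hoc power analysis with 95% confidence intervals for the arm differences and the pooled CNP rate. At a 30% rate these would be about ±32 and ±13 points. Size the larger study from these intervals and a stated effect of interest.

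If the investigators want to keep an option to extend, they should base it on a pre-specified effect and the pooled, arm-blind CNP rate, with 60 as the cap. They should also reconcile View 4 with View 4.1 on the primary endpoint.

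The change is to wording only. Its cost is that the final CNP result waits for the last 12-month survey, and that enrolment can no longer be extended on the between-arm result.

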View: 8 Methods of Recruitment and Retention

Recruitment Methods and Materials used for Retention**1.0 * Select recruitment methods used on this study:**

Name

- Mail Campaign
- Referral by independent source
- Advertising such as fliers, letters, or ads (newspaper, TV, radio)
- Web Site
- Research registry
- Selected from pre-existing records
- Pre-existing relationship with participants

Other

If Other Methods Specify:

Subjects will be recruited based on their referral to the Interdisciplinary Medical Perioperative Assessment Consultation Treatment (IMPACT) clinic, as described below.

2.0 * Specify how subjects will be identified and how study eligibility will be determined:

A total of 48 (16 in each of three groups) patients undergoing either inguinal (including femoral) or ventral (including umbilical) herniorrhaphy that requires general anesthesia in the operating room will be enrolled in the study with continuous sampling. A patient will be considered enrolled in the study when they have passed initial screening questions, signed the consent form, and been randomized. Subject recruitment will occur through In-person or e-consult paths, both described below.

IMPACT In-person Visit

General surgery patients are referred to the Interdisciplinary Medical Perioperative Assessment Consultation Treatment (IMPACT) clinic for routine medical and functional evaluations prior to surgery. These include patient history, physical examination, and other evaluations in routine patient care that do not typically include the detailed pain status questionnaires to be used in this study. During the in-person consult, [name] reviews each patient's medical record, determining if the patient is medically optimized and ready for their scheduled surgery. At this time, [name] will also screen the patient's medical record to determine if the patient meets the study's inclusion and exclusion criteria and could be a potential candidate. If so, she will briefly describe the study as follows:

"Several of the physicians of our anesthesia department are interested in understanding how the amount of pain you feel after a surgery to repair a hernia can be influenced by the type of anesthesia medications you receive during your surgery. For this study, you would receive a standard anesthetic combination, but it would be randomly chosen from several standard approved combinations now available. They would like to ask you questions about your pain both before and after your surgery (which they can do over the phone). Do you think you might be interested in participating? [If "no", STOP] [If "yes", CONTINUE]

With your permission, I would like to share the details of your upcoming surgery and the history I collected with them so that they can discuss this study with you to see if you are interested. To do so, I need your consent to share this information."

[name] will then ask for the patient's approval to share the patient's name, scheduled surgery, and IMPACT Pre-operative evaluation with [name] (study PI). If the patient agrees, [name] will also provide the potential subject with a copy of the Informed Consent form for their review. Waivers of HIPAA, informed consent, and documentation of informed consent have been requested for the screening and sharing of information described above.

[name] will then be notified of the patient's possible interest via phone call or secure, encrypted VA email. [name] will contact (in person if possible; if not, via telephone) the patient to explain the procedures of the study using the attached script if they are eligible. All patient questions will be answered, and the patient will be told that all signatures will be obtained on the informed consent document on the day of surgery after any additional questions are answered.

When the patient presents on the day of surgery, [name] will review the patient's information, inquire about any health status or operative plan changes, and obtain informed consent. The patient's name will be added to the master list of subjects once they consent to screening. The master list of subjects will be stored electronically on the VAPHS network, and this list will only be viewable to the PI. The patient will then be randomized to one of three anesthetic technique protocols (TIVA-K, TIVA-R, or BIA) using a computer-generated random numbers table. Following this, the baseline information (including the demographics and pain survey scores included on the research study forms) will be collected.

IMPACT e-Consult

Instead of in-person consult for general surgery patients, e-consults are sometimes performed by the IMPACT team via phone for routine medical and functional evaluations prior to surgery. These include examining the electronic medical record for patient history and other evaluations in routine patient care that do not typically include the detailed pain status questionnaires to be used in this study. During the e-consults for hernia repair surgery, the IMPACT staff member will briefly state the following:

"Several of the physicians of our anesthesia department are interested in understanding how the amount of pain you feel after a surgery to repair a hernia can be influenced by the type of anesthesia medications you receive during your surgery. For this study, they would like to ask you questions about your pain both before and after your surgery (which they can do over the phone). If you are interested in participating in this study, please contact [name] at [contact] for more details."

The IMPACT staff member will not screen for study eligibility; all patients for hernia repair will be given this information. Patient contact with [name] is being requested due to her availability via telephone during business hours. If the patients are interested and contact [name], she will screen the patient's medical record to determine if the patient meets the study's inclusion and exclusion criteria and could be a potential candidate. If so, she will briefly describe the study as follows:

"Several of the physicians of our anesthesia department are interested in understanding how the amount of pain you feel after a surgery to repair a hernia can be influenced by the type of anesthesia medications you receive during your surgery. For this study, you would receive a standard anesthetic combination, but it would be randomly chosen from several standard approved combinations now available. They would like to ask you questions about your pain both before and after your surgery (which they can do over the phone). Do you think you might be interested in participating? [If "no", STOP] [If "yes", CONTINUE]

With your permission, I would like to share the details of your upcoming surgery and the history that I collected with them so that they can discuss this study with you to see if you are interested. To do so, I need your consent to share this information. They will also mail a copy of the consent form to you so that they can go over it with you."

[name] will then obtain verbal HIPAA consent prior to sharing the patient's name, scheduled surgery, and IMPACT Pre-operative evaluation with [name] (study PI). Waivers of HIPAA, informed consent, and documentation of informed consent have been requested for the screening and sharing of information described above.

[name] will then be notified of the patient's possible interest via phone call or secure, encrypted VA email. [name] will contact (via telephone) the patient to explain the procedures of the study using the attached script if they are eligible. All telephone contacts will begin by referring to the subject's (possible) participation in the research study. All patient questions will be answered. The patient will be told that while all signatures will be obtained on the informed consent document on the day of surgery after any additional questions are answered.

When the patient presents on the day of surgery, [name] will review the patient's information, inquire about any health status or operative plan changes, and obtain informed consent. The patient's name will be added to the master list of subjects once they consent to screening. The master list of subjects will be stored electronically on the VAPHS network, and this list will only be viewable to the PI. The patient will then be randomized to one of three anesthetic technique protocols (TIVA-K, TIVA-R, or BIA) using a computer-generated random numbers table. Following this, the baseline information (including the demographics and pain survey scores included on the research study forms) will be collected.

3.0*** Provide the location (or locations) of the sites where participants will be recruited:**

For the in-person visit path, recruitment will begin in the IMPACT clinic, continuing when the patient talks with [name] either in-person or over the telephone. There will be a check for any pertinent changes that may have occurred in each patient's health information and surgical plan being performed in the Same-Day Surgery holding area on the day of surgery prior to the informed consent document being signed.

For the e-consult path, recruitment will occur via phone, with an informed consent being signed (and a check for any pertinent changes that may have occurred in each patient's health information and surgical plan being performed) in the Same-Day Surgery holding area on the day of surgery.

4.0**Please include information regarding any advertisements (print, TV, radio, etc) that will be used to recruit subjects including a general description of where this information will be posted:**

None.

5.0**Please UPLOAD the documents that will be used for recruitment and an introductory statement or letter to accompany consent for those studies obtaining written informed consent using methods such as fax, email or mail (if applicable). Please also upload any screening/recruitment questions that will be verbally asked of potential research subjects. Also, if you will be providing any retention materials, please upload them here.**

Name Reviewer

Modified Date

Version Number

There are no items to display

ID: Pro00000878

View: 9 Informed Consent

Informed Consent**1.0***** Indicate the types of consent that will be involved in this study (check any or all that apply):**

Informed Consent Category

Written/signed consent by subject

Waivers are being requested.

Verbal consent or written information sheet(Requires a Waiver of Documentation of Informed Consent - see below)

2.0*** Waivers: If you are applying for any waivers of consent (check any or all that apply):**

Name

 Waiver of Informed Consent **Waiver of HIPAA Authorization** **Waiver of Documentation of Informed Consent (telephone consent, verbal script)** No Waiver at all**3.0***** Will this study include non-English speaking participants?** Yes **No**

ID: Pro00000878

View: 9.1 Waiver of HIPAA

You have indicated you are requesting a waiver of HIPAA.**1.0 * Is the request only for Screening/Recruitment purposes?** Yes No

If yes, please describe your screening/recruitment method:

As described in Section 8: General surgery patients are referred to the Interdisciplinary Medical Perioperative Assessment Consultation Treatment (IMPACT) clinic for routine medical and functional evaluations prior to surgery. These include patient history, physical examination, and other evaluations in routine patient care that do not typically include the detailed pain status questionnaires to be used in this study. During the in-person consult, [name] reviews each patient's medical record, determining if the patient is medically optimized and ready for their scheduled surgery. At this time, [name] will also screen the patient's medical record to determine if the patient meets the study's inclusion and exclusion criteria and could be a potential candidate. If so, she will briefly describe the study, and ask for the patient's approval to share the patient's name, scheduled surgery, and IMPACT Pre-operative evaluation with [name] (study PI). [name] will ask screening questions regarding prior anesthesia and chronic pain. Waivers of HIPAA, informed consent, and documentation of informed consent have been requested for the screening and sharing of information described above.

Occasionally, e-Consults are used for patient pre-operative evaluation by the IMPACT staff. In this case, the IMPACT staff member will briefly state the following:

"Several of the physicians of our anesthesia department are interested in understanding how the amount of pain you feel after a surgery to repair a hernia can be influenced by the type of anesthesia medications you receive during your surgery. For this study, they would like to ask you questions about your pain both before and after your surgery (which they can do over the phone). If you are interested in participating in this study, please contact [name] at [contact] for more details."

The IMPACT staff member will not screen for study eligibility; all patients for hernia repair will be given this information. Patient contact with [name] is being requested due to her availability via telephone during business hours. If the patients are interested and contact [name], she will screen the patient's medical record to determine if the patient meets the study's inclusion and exclusion criteria and could be a potential candidate. [name] will then inform the patient of their eligibility and if eligible, obtain verbal HIPAA consent prior to sharing the patient's name, scheduled surgery, and IMPACT Pre-operative evaluation with the [name] (study PI). [name] will ask screening questions regarding prior anesthesia and chronic pain. Waivers of HIPAA, informed consent, and documentation of informed consent have been requested for the screening and sharing of information described above.

If no, the request is for the full study (e.g. retrospective chart reviews and certain observational studies)

Please describe the types of records and/or databases to be accessed:

THE IDENTIFIABLE INFORMATION BEING REQUESTED:

Note: If participants will be receiving payment and HIPAA Authorization is not being obtained, you must select Names, Addresses and Social Security Numbers as that information will be disclosed for payment purposes.

2.0 * Identifiable Information per HIPAA Definition

Name	
None	
Account numbers	
Biometric identifiers, including finger and voice prints	
Certificate/license numbers	
Device identifiers and serial numbers	
 Elements of dates (except year, for example, date of birth, admission date, discharge date, date of death, date of procedures; and all ages over 89)	
Email Address	
Fax Numbers	
Full-face photographic images or any comparable images	
Geographical subdivisions smaller than a State (street address, city, county, precinct, zip code, and their equivalent geocodes, except for the initial three digits of a zip code)	
Health plan beneficiary numbers	
Internet Protocol (IP) address numbers	
Medical Record Numbers	
 Name or any derivative of name such as initials	
 Social Security Numbers	
 Telephone Numbers	
URLs (Web Universal Resource Locators)	
Vehicle identifiers and serial numbers, including license plate numbers	
Any other unique identifying number, characteristic, or code (Note: The study ID number, code or other means of record identification is not considered one of the identifiers that must be excluded for de-identification)	

3.0 * Patient Protected Health Information:

Name	
 Demographic Information (e.g., Name, Address, Phone Number, Social Security Number)	
Billing and Payment Information	
 Hospital or Medical Records	
 History and Physical Exam Notes	
Mental Health Records	
Data Previously Collected for Research Purposes	
 Progress Notes	
Consultation Reports	
Laboratory Test Results	
Operative Reports	
Other	

Please indicate the 'Other' Patient Protected Health Information:

4.0 Other Health Information:

Name

There are no items to display

ID: Pro00000878

View: 9.1.1 Waiver of HIPAA - More Information

Waiver of HIPAA- More Information

1.0 *** Describe how the identifiable information is to be used and/or disclosed only by members of the research team and the following persons (identify with specificity and justify the need to disclose the information to anyone outside the VHA.) Note: If participants will be receiving payment and HIPAA Authorization is not being obtained, you must also describe this disclosure to representatives of the VA for administrative purposes here.**

Also describe how this activity meets the “minimum necessary standard” described in the HIPAA Privacy Rule:

The waiver is:

- A. For [name] to prescreen the medical records for potential eligibility (inclusion/exclusion criteria).
- B. To pass along information (i.e., patient's name and contact information, scheduled surgery, and IMPACT Pre-operative evaluation) to the PI of individuals who agree to be contacted.

This procedure meets the “minimum necessary standard” as described in the HIPAA Privacy rule due to the fact that [name] would be reviewing the medical record for the information for clinical reasons and the PI will only receive the information necessary to contact eligible and interested patients.

The proposed study poses minimal risk to the privacy of the subjects because...

2.0 *** Describe how the identifiable information will be protected from improper use or disclosure by (detail how this will be accomplished including the limitations of physical or electronic access to the information and other protections):**

If the patient agrees to further contact with the research team, the [name] will then notify [name] via in-person communication or through secure, encrypted VA email.

3.0 *** Describe how the identifiers will be destroyed at the earliest opportunity consistent with the research (discuss the timeframe or the reasons the identifiers must be retained, including health or research justifications or any legal requirement to retain them) (Note: At this time, identifiers used for research screening and all other screening records must be retained indefinitely and this must be documented by checking “Other” below):**

After contacting the potential subject, the PI will delete the email from his account. If the subject agrees to participate after receiving the complete study information, then the patient's name will then be added to the master list of subjects. The master list of subjects will be stored electronically on the VAPHS network, as described elsewhere, and this list will only be viewable to the PI.

All research records will be maintained in accordance with the Veterans Health Administration (VHA) Records Control Schedule. Paper records will be disposed of using methods deemed appropriate by the VAPHS Privacy Officer, and all electronic data will be sanitized using methods rendered appropriate by the VAPHS ISO.

